## **4.4 Early Withdrawal of Subjects**

### **4.4.1 When and How to Withdraw Subjects**

Subjects may withdraw from the study at any point without consequence to their future care. If consent is withdrawn while RIC cycles are being administered, regardless of reason, the autoRIC® device will be stopped and removed from the patient. There are no anticipated risks to patients from abrupt termination of the RIC procedure. Care providers (i.e. paramedics or ED physicians) may terminate RIC if the patient becomes severely hypotensive (SBP < 90 mm Hg), experiences an unsafe drop or rise in blood pressure, or for other safety reasons at the discretion of the provider. Discontinuation of RIC prematurely will be documented as a primary endpoint. Specific reason(s) for discontinuation whether related to patient tolerability or safety will be documented to address secondary objectives and will be recorded for adverse event reporting.

### **4.4.2 Data Collection and Follow-up for Withdrawn Subjects**

Study objectives do not require subject follow-up past EMS response, ambulance transport, and ED stay. Withdrawn subjects will be asked for primary reason(s) for terminating participation in the study.

## **5 Study Device**

### **5.1 Description**

The autoRIC® is a device system that automatically delivers cycles of RIC. Once placed on the upper arm, the programmed device is initiated by pressing a single start button with each cycle consisting of a 5-min period of a cuff inflated to 200 mm Hg followed by a 5-min period of the cuff deflated. The system is programmed to operate a total length of 35 minutes since the final 5-min period of deflation is technically no action or intervention. Additional details of the investigational device are provided in Section 1.2.

### **5.2 Procedure Regimen**

The autoRIC® is programmed to deliver four cycles of RIC with each cycle consisting of a 5-min period of a cuff inflated to 200 mm Hg followed by a 5-min period of the cuff deflated for a total procedure time of 40 minutes. At any time, RIC can be terminated by pressing the stop button or physically removing the cuff-device system from the arm.

For this study population, RIC is not considered a treatment since no clinical benefit is expected in patients not undergoing reperfusion, as in STEMI patients receiving PCI, or otherwise at risk for ischemia-reperfusion injury. Therefore, rather than testing a treatment effect, the autoRIC® in this study is being evaluated for feasibility of prehospital delivery and operational efficiency.

### **5.3 Method for Assigning Subjects to Treatment Groups**

Since this is a single-arm, pilot study, all subjects will receive the study device. There will be no assignment or randomization of treatment groups.

### **5.4 Preparation and Administration of Study Device**

The autoRIC® device will be stored in a locked cabinet at the EMS station while not in use for the study. At the start of each 6AM-6PM enrollment period, the paramedic will ensure the device is fully charged. The charging cradle will be set up in the ambulance unit, and, after each use, the device will be returned to charging cradle. If necessary, up to 3 consecutive patients can be treated on a full charge, but every effort will be made to keep the device fully charged.

The autoRIC® will be administered according to the operator's manual. Briefly, once the paramedic determines the appropriate cuff size, the applicator cuff, with control unit, is placed directly on the upper arm without any clothing, tubing, or other foreign object between the cuff and patient. If IV access has been established in an arm as part of providing usual care, the device will be applied to the opposite arm. Blood pressure measurements, for usual care, will be made in the arm with the IV in place.

Once the device is in place and the paramedic presses the "Start" button, s/he will confirm all LEDs illuminate to ensure the device is working properly. After the fourth and final cuff inflation, the device can be removed from the patient for the final 5-min deflation period. The applicator cuffs are single-use, and therefore, they will be disposed according to OCES and UNC's medical waste policy.

The paramedic will retrieve the device after each use. If the ambulance unit is back in service prior to the completion of four cycles, the device will be returned to the ambulance by the SC or other key study personnel.

### **5.5 Subject Compliance Monitoring**

Device start and stop times will be recorded by paramedic or SC, as appropriate. If the autoRIC® is prematurely terminated for any reason, the number of cycles completed and progress of the current cycle will also be recorded as indicated by LED lights on the device. This information will be captured as the primary study endpoint.

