### **3.2 Primary Outcomes**

To assess the feasibility of delivering RIC in the prehospital setting, the primary endpoint will be the completion of 4 cycles of RIC without interruption using the autoRIC® device. We will also examine total time (in minutes) and number of cycles that RIC was administered.

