When the patient and paramedic crew arrive to the ED, providers in the ED will first provide standard care. The SC will collect study forms and other documentation from the paramedic. Once initial care (e.g., provider assessment, repeat ECG, lab draws) is completed and the patient is placed under observation for further work-up, the SC will approach the patient, with approval from the treating physician, to complete the full informed consent process and describe additional data collection including medical record review and abstraction and collection and storage of blood samples for future testing. The SC will assess comprehension based on the patient's ability to restate key study objectives and procedures and anticipated risks and benefits. If the patient consents, both SC and patient will sign two copies of the informed consent form (see Appendix D), one for study documentation and the other for the patient. If the patient refuses, RIC will be stopped and data collected up to that point will be de-identified and retained to address primary and secondary study objectives.

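### Four completed cycles are never read off the device for presumed completers, so an unnoticed fault, interruption or untimed removal may be counted as completion of the primary endpoint

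*Combined protocol and SAP*

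**What the plan says.** Section 3.2 defines the endpoint: "the primary endpoint will be the completion of 4 cycles of RIC without interruption using the autoRIC® device". It adds two supporting measures: "We will also examine total time (in minutes) and number of cycles that RIC was administered".

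Section 5.5 says how these are captured. For all subjects: "Device start and stop times will be recorded by paramedic or SC, as appropriate". For some subjects there is more: "If the autoRIC® is prematurely terminated for any reason, the number of cycles completed and progress of the current cycle will also be recorded", taken from the lights on the device. The section closes: "This information will be captured as the primary study endpoint".

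The only device check stated for every subject comes at the start, in Section 5.4, where the paramedic presses the button and "s/he will confirm all LEDs illuminate to ensure the device is working properly". No section asks for a reading of the lights, or any other device record, at the end of a run that is believed to be complete.

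On the setting, Section 2 expects cycling to continue into the ED stay. Section 4.3 says that on arrival "providers in the ED will first provide standard care", and that the study coordinator approaches the patient for written consent once initial care is done. Section 5.2 says that at any time "RIC can be terminated by pressing the stop button or physically removing the cuff-device system from the arm". Section 4.4.1 requires premature discontinuation and its reasons to be documented.

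**The concern.** The device's own evidence on cycles is collected only after someone has recognised that a run failed. In every other subject, two handwritten times must establish both that four cycles were delivered and that nothing interrupted them. Times can show that a run was too short. They cannot show that the cuff cycled properly while it was on the arm, and they show an early removal only if it was timed when it happened.

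This bears on the study's single primary endpoint, which is meant to inform a later trial. It also affects the number of cycles and total minutes in Section 3.2, which come from the same record.

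**Working it through.** **1. The plan's own figure.** Inputs from Section 7.1: n = 50, completion 0.80. Wald half width = 1.96 × √(0.80 × 0.20 / 50) = 0.1109, which agrees with the stated 0.11. This covers sampling error only and makes no allowance for misclassified runs.

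**2. What the record can and cannot show.**

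| Event | Start and stop times | Light reading under 5.5 |
|---|---|---|
| Early stop, recognised and timed | Short run visible | Taken |
| Removal in the ED, true stop time written | Short run visible | Taken, if recognised as early |
| Removal in the ED, not timed, retrieval time written instead | May look like a full run | Not taken |
| Fault or interruption, cuff left on the arm and not noticed | May look like a full run | Not taken |
| Full run | Full run | Not taken |

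On the present record, the third and fourth rows cannot be told apart from the fifth.

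**3. The time check has no threshold.** Section 5.1 gives a programmed length of 35 minutes: 4 × 5 inflated + 3 × 5 deflated = 35. Section 5.2 gives a procedure of 40 minutes: 4 × 10 = 40. Section 5.4 allows removal after the fourth inflation. No section states the recorded duration that counts as completion.

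**4. Effect per subject.** 1/50 = 0.02. With 11 true non-completers, the true rate is 39/50 = 0.78, and one missed case gives 40/50 = 0.80. With 10 true non-completers (0.80), missing 1 to 3 of them gives 41/50 to 43/50, or 0.82 to 0.86.

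**5. Sensitivity to the miss rate.** The documents give no miss rate, so m, the share of true non-completions that go unnoticed, is an assumption. Full runs are taken as correctly classified. Observed rate = p + (1 − p) × m. The last columns give the probability that a binomial count with n = 50 and that observed rate reaches at least 40.

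| True p | m = 0 | m = 10% | m = 25% | m = 50% |
|---|---|---|---|---|
| 0.70: observed rate | 0.70 | 0.73 | 0.775 | 0.85 |
| 0.70: chance of ≥ 40/50 | 0.079 | 0.170 | 0.411 | 0.880 |
| 0.75: observed rate | 0.75 | 0.775 | 0.812 | 0.875 |
| 0.75: chance of ≥ 40/50 | 0.262 | 0.411 | 0.670 | 0.958 |

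These rows show how the result would respond to missed cases. They do not estimate how many there will be.

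**The case against.** The strongest reply is that the plan already has safeguards. Start and stop times are taken for all subjects, so a removal at 20 minutes with a true stop time is visibly short of either 35 or 40 minutes. Section 4.4.1 requires early discontinuation to be documented with reasons, including when ED physicians end it. Under Section 6.2 the coordinator meets the team in the ED, takes over study responsibilities and may be at the bedside while cycling continues. Section 10.1 has weekly review of procedure quality and data accuracy. The CRF and operating procedures are not among the documents, so they may ask for more than Section 5.5 does. All of this stands, and it narrows the problem to faults or interruptions nobody notices and removals nobody times.

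It is also fair that the interpretation does not turn on one subject alone. Section 7.2 compares the proportion and its 95% CI with 0.80, without a test. Wald intervals for 39/50 (about 0.67 to 0.89) and 40/50 (0.69 to 0.91) both contain 0.80.

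Three stronger readings are tempting and are not supported:

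- A reader might infer that the plan scores success by default. No section contains such a rule; the plan is silent on how an unverified run is classified.
- A reader might infer that the coordinator is absent during initial ED care. Section 4.3 delays the consent approach; it does not say the device goes unobserved. Nor does any section require continuous observation.
- A reader might infer that all error favours completion. The cases described here do, but a full run taken off at 35 minutes and judged against 40, or a start time written late, would err the other way.

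**Conclusion.** The point holds as a gap in how the primary endpoint is ascertained. For subjects without a recognised early stop, nothing in the documents positively confirms four uninterrupted cycles, and some failed runs may be counted as complete.

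The size is unknown. What can be stated is 2 percentage points per missed case with a denominator of 50, on top of the sampling error in the 0.11 half width. The larger shifts tabulated above depend wholly on the assumed miss rates. This does not show that the result will be biased upward overall. It is a case for a cheap improvement in measurement before enrolment starts.

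**What to change.** Amend Section 5.5, and the CRF to match, as follows:

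1. For every subject, whoever removes the device records the light status and the actual time cycling ended or the device came off, not the time it was retrieved.
2. Where the lights were read, score four completed cycles from them.
3. Where they were not read, classify the run from start and stop times against a single stated run time, and report it as unverified. This requires the sponsor first to reconcile the 35 minutes in Section 5.1 with the 40 minutes in Section 5.2.
4. Give a sensitivity analysis that counts unverified runs as not completed.

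Unread runs should not be counted as failures in the primary analysis: that would penalise full runs for a missed form entry and push the estimate the other way.

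Before the form is finalised, check in the operator's manual that the lights still show the cycle count after a full run. The documents describe that reading only for early stops.

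The cost is one extra CRF field per subject, for a reading the plan already uses in some of them. Completion may read slightly lower.

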### **5.6 Prior and Concomitant Therapy**

Medications administered by the paramedic will be collected. It is expected these will primarily consist of aspirin and nitroglycerin for management of chest pain.

### **5.7 Packaging**

The autoRIC® devices will be shipped with their standard packaging and product labeling.

### **5.8 Receiving, Storage, Dispensing and Return**

#### **5.8.1 Receipt of Devices & Supplies**

The required number of autoRIC® devices (three total – two for study use and one for training and back-up) will be shipped from the supplier CellAegis Devices, Inc. (Toronto, Canada) to the study PI. Upon receipt of the study devices and supplies, an inventory will be performed, and a device receipt log filled out and signed by the person accepting the shipment. Designated study staff will count and verify that the shipment contains all the items noted in the shipment inventory.

### 5.8.2 Storage

According to technical specifications, the autoRIC® can be transported and stored in an ambient temperature range of -4 °F to 122 °F and a relative humidity range of 0% to 85%. When not in use, devices will be stored in locked cabinets.

### 5.8.3 Dispensing of Study Device

Devices will be dispensed to study paramedics by the PI. In a device accountability log, the PI and SC will keep track of each device and document each use including the size of the single-use applicator cuff. Using this log, the study PI and SC will monitor the remaining supply of each cuff size and will re-order as needed.

### 5.8.4 Return or Destruction of Study Device

At the completion of the study, the autoRIC® devices will be stored in a locked cabinet at the study site. If no future studies are planned, the devices will be shipped back to the supplier CellAegis Devices, Inc.

## 6 Study Procedures

This study requires a single visit. Table 1 illustrates the flow of study procedures throughout the study visit and additional data collection following the visit. All study procedures involving direct patient interaction will occur in the ambulance and ED. Prior to the onset of subject enrollment, study paramedics will undergo training on the study protocol and standard operating procedures.

### 6.1 Ambulance Transport

During ambulance transport, the study paramedic will record information on a paper Case Report Form (CRF). The CRF will be pre-populated with a unique subject identifier (ID). The paramedic will document general information, including incident date-time, patient name and contact information, and will also complete the screener. As previously described, eligible patients interested in learning more about the study will be connected to the SC by telephone. After verbal consent is obtained over the telephone, the paramedic will prepare the autoRIC® device (e.g. check battery, determine appropriate cuff size). The device will be placed on the patient and started according to the operator's manual. Along the way, the paramedic will record the time of RIC initiation and other key time points needed to compute secondary endpoints. While RIC is being administered, the paramedic will note observations and feedback on the recruitment process, operating the device, patient safety or adverse events, and any delays incurred due to RIC or other study procedures. If RIC is terminated prematurely, the paramedic will document the primary reason(s).

Table 1. Flow of Study Procedures and Data Collection

Study Procedures	Study Visit		Post-Visit
	Ambulance Transport	Emergency Department	
Standard care (paramedic and ED staff)	X	X	
Screening	X		
Initial verbal consent by telephone	X		
RIC intervention*	X → →	→ → →	
Safety and adverse event reporting	X	X	
Full written informed consent		X	
Blood collection, preparation, and storage		X	
Patient interview			X
Additional Data Collection			

Medical record review		X
Cardiac monitor report retrieval		X
Blood analysis (post-hoc)		X

\*may overlap with other study procedures

## 6.2 Emergency Department

The SC will meet the paramedic team and patient in the ED. At this point, the paramedic will hand over the CRF to the SC and transfer study responsibilities, including safety and adverse event reporting. After initial ED care and while the patient is under observation and awaiting further work-up, the SC will complete the full informed consent process. This process may occur while the RIC procedure is still in progress. Although the study intervention is already started, the subject will have the opportunity to decline participation in the patient interview; access to medical records and other clinical data; and collection and storage of blood specimens for future testing. The SC will assess comprehension of consent by asking the subject to describe the purpose of the study, foreseeable risks and benefits of study participation, the possibility of unanticipated risks, and other elements of informed consent. No additional study procedures will occur until the consent process is complete and both patient and SC sign necessary consent forms.

After consent is obtained, a blood sample of 15 mL will be collected by Department of Emergency Medicine clinical research staff using existing venous access. When possible, this sample will be obtained with other blood draws taken as part of usual care. Blood for plasma will be collected using an EDTA tube (e.g., BD Vacutainer® plastic blood collection tube). Tubes will be labeled with the date and time of collection and the unique subject ID but no other identifiers. Specimens will be prepared according to standard procedures for separating plasma and will be stored in a -80 °C freezer located in a locked area in the department's research laboratory. No blood testing or analyses will be done under this protocol. In future studies, these samples may be used to investigate biomarkers and molecular pathways involved in the mechanism(s) of RIC.

Using an interview guide, the SC will elicit patient feedback on undergoing the RIC procedure (e.g., "what did it feel like?", "how would you describe to someone else?"). The SC will note subject responses in the CRF.

## 6.3 Post-Visit

There will not be any post-ED visits required of the subject. All additional study data collected following the study visit will be obtained by the SC or other study personnel via retrospective chart review and will not require subject interaction. Subjects will however be contacted after 48 hours, either by telephone or in-person depending on location, to assess for adverse events related to study participation.

Following the study visit, the SC will enter data from the CRF into a secure, web-based database (Research Electronic Data Capture, REDCap). Additional relevant clinical data from the subject's medical record (e.g. medical history, diagnoses, and lab results) and the EMS patient care report will also be abstracted and entered into the database. Furthermore, automatic reports from the EMS agency's LIFEPAK® 12 cardiac monitor will be retrieved and saved for potential additional analyses of vital signs and ECG patterns. Frozen plasma specimens may be thawed and tested in future research exploring mechanisms of RIC.

[figure not shown]
# 7 Statistical Plan

## 7.1 Sample Size Determination

Since the primary objective of this pilot study is to assess feasibility and optimize methods, no formal statistical hypothesis testing will be performed. A 5-month enrollment period is appropriate given limited time and resources,

and will be sufficient to enroll the target of 50 patients. This sample size would produce a 95% (confidence interval) CI half width of 0.11 given the frequency of RIC completion is 0.80 (primary hypothesis). Sample sizes larger than 50 provide only marginal gains in precision (Figure 4).

**Figure 4. Statistical precision in the primary endpoint by sample size**

## 7.2 Statistical Methods

Summary statistics (e.g., proportions, medians) will be used to characterize the study sample with respect to patient demographic and clinical characteristics and process factors related to the RIC procedure. The primary outcome measure, as previously discussed, will be the frequency (i.e., proportion) of all subjects receiving RIC who completed 4 cycles. The primary hypothesis will be evaluated by comparing the proportion and its 95% CI to the predetermined benchmark of 0.80. Since this is a pilot study to collect feasibility data, no inferential statistical tests will be performed. Descriptive analyses will compare patient characteristics (demographics, medical history, clinical factors) and process measures (timing of study procedures) between RIC completers and non-completers.

Qualitative data from paramedic feedback and patient interviews will be analyzed for general themes regarding key aspects of study methodology. Themes will be derived from qualitative text and related to quantitative demographic and clinical characteristics in a mixed methods analysis using the software MAXQDA (VERBI GmbH, Berlin, Germany). A full analysis plan will be developed in consultation with UNC mixed methods research experts.

## 7.3 Subject Population for Analysis

For both primary and secondary objectives, any subject consented and enrolled to receive RIC will be analyzed.

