### **3.3 Secondary Outcomes**

Secondary Objective #1: Patient enrollment and protocol efficiency

- a) Eligibility and participation rates and corresponding reasons for ineligibility and refusal
- b) Timing of study procedures
  - i) Time to onset of transport from initial arrival on scene
  - ii) Time to start screening from onset of transport
  - iii) Time to screen, whether eligible or not
  - iv) Time to recruit, whether enrolled or not
  - v) Time to start the autoRIC® device once consent is obtained

Secondary Objective #2: Paramedic acceptability

- a) Paramedics' feedback on the delivery of RIC and other study procedures

Secondary Objective #3: Patient tolerability

- a) Documentation of anticipated adverse events including RIC discontinuation due to discomfort
- b) Patients' experiences while undergoing the RIC procedure

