#### 4.3 Subject Recruitment and Screening

Two full-time OCES ground ambulance units that provide advanced life support (ALS) services to the southern part of Orange County and typically transport to UNC Medical Center will be used for this study. Paramedics assigned to these units will be responsible for assessing and screening patients during the enrollment period from 6am-6pm, Monday-Friday. So that arrival to the UNC ED is not delayed, screening and recruitment will not begin until the patient is en route to the hospital and given usual care, at the discretion of the paramedic. Paramedics will assess the patients' capacity to consent for the study following their usual approach to assessing patients' capacity to make medical decisions, e.g. accept or refuse treatment.

In a two-stage screening and recruitment process (Figure 3), the study paramedic will first assess and determine whether the patient meets all eligibility criteria. If the patient is not eligible, the paramedic will document the primary reason(s) on a screener form. If the patient is eligible, the paramedic, using a suggested script (see Appendix B), will offer the patient an opportunity to learn more about the study by telephone call with a study coordinator (SC). If the patient agrees, the paramedic will hand the patient a study information sheet (see Appendix C) and will call the SC or back-up key study personnel using a dedicated cellular telephone. In the second screening stage, the SC will confirm with the paramedic that the patient is eligible. Then the patient will be handed the telephone. The SC, following a script (see Appendix B), will provide basic information about the purpose of the study, RIC procedure, and risks and benefits of participating and will answer any questions that patient may have. To assess consent capacity, the SC will ask the patient to describe the RIC procedure and whether study participation will have any effect on medical care received. A patient with capacity to consent will be invited to participate. If the patient responds in the affirmative, this will be considered verbal consent, and the SC will instruct the paramedics to apply and start the autoRIC® device. This telephonic method to obtain consent in the field is based on a strategy developed and tested in prior prehospital trials by Saver et al.

Figure 3. Flow chart of recruitment and enrollment

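### Does the single analysis population in section 7.3 shut out the screened and refusing patients that Secondary Objective 1 needs?

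*Combined protocol and SAP*

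**What the plan says.** Section 7.3 consists of one sentence: "For both primary and secondary objectives, any subject consented and enrolled to receive RIC will be analyzed".

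Section 3.3 lists the outcomes for Secondary Objective 1. Item (a) is "Eligibility and participation rates and corresponding reasons for ineligibility and refusal". Among the timings in item (b), (iii) is "Time to screen, whether eligible or not" and (iv) is "Time to recruit, whether enrolled or not". Item (b)(v), the time to start the device, is by contrast tied to consented patients ("device once consent is obtained").

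Section 4.3 describes two stages. The paramedic screens first: "If the patient is not eligible, the paramedic will document the primary reason(s) on a screener form". An eligible patient is then offered a telephone call with the study coordinator ("If the patient agrees, the paramedic will hand the patient a study information sheet"). The coordinator checks again: "In the second screening stage, the SC will confirm with the paramedic that the patient is eligible". The coordinator then assesses capacity and invites the patient to take part.

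For the primary outcome, section 2.1 refers to patients in whom RIC was initiated and section 7.2 to subjects receiving RIC. Section 5.3 states that every subject will receive the device. Section 7.1 gives a 95% CI half-width of 0.11 for 50 patients at a completion frequency of 0.80, with no hypothesis test.

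**The concern.** Section 7.3 is the only text under the heading for analysis populations, and it expressly covers the secondary objectives. A patient who is ineligible or who refuses is, by definition, not consented and enrolled. If the sentence is a restriction, items 1(a), 1(b)(iii) and 1(b)(iv) cannot be produced as section 3.3 defines them.

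Section 2.2 says the secondary objectives are there to inform a future trial, and eligibility and participation rates come first among them. In a pilot without hypothesis tests, such descriptive rates are a main product.

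Two related questions arise. Patients can be lost at several points between the paramedic's offer and verbal consent, so the participation rate depends on which of them are counted. And section 7.3 (consented and enrolled) is worded differently from sections 2.1 and 7.2 (initiated or received), which could shift the primary denominator if someone consents but never starts RIC.

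**Working it through.** **1. The plan's own figure.** Inputs from section 7.1: n = 50, p = 0.80, 95% confidence. Half-width = 1.96 × √(0.80 × 0.20 / 50) = 0.1109, which matches the stated 0.11. It concerns the primary outcome only and does not depend on how Objective 1 is populated.

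**2. Section 7.3 read as exclusive.** Eligibility and participation are each 50/50 = 100%, with no reasons to tabulate. Set beside the rest of the plan, this reading fails:

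| Item | What the plan asks for | Possible if 7.3 is exclusive? |
|---|---|---|
| 1(a) | rates, with reasons for ineligibility and refusal | no |
| 1(b)(iii) | screening time, ineligible patients included | no |
| 1(b)(iv) | recruitment time, non-enrolled patients included | no |
| 1(b)(i), (ii), (v) | other timings | yes |
| Objective 2 | feedback from paramedics, who are not RIC subjects | no |

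The last row is telling. An exclusive rule would rule out all of Objective 2, which cannot be intended. Read as a minimum (every enrolled subject is kept in), section 7.3 fits all five rows.

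**3. The participation denominator.** The documents give no losses by stage, so both cases below are assumptions, each with 50 consenting. Losses are listed in the order: decline the offer / found ineligible or lacking capacity by the coordinator / refuse on the call.

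| Denominator | 67 offered, losses 6/3/8 | 100 offered, losses 20/10/20 |
|---|---|---|
| All offered | 50/67 = 74.6% | 50/100 = 50.0% |
| Offered, less coordinator-ineligible | 50/64 = 78.1% | 50/90 = 55.6% |
| Reached the coordinator | 50/61 = 82.0% | 50/80 = 62.5% |
| Invited | 50/58 = 86.2% | 50/70 = 71.4% |

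The spread is 86.2 − 74.6 = 11.6 points in the first case and 71.4 − 50.0 = 21.4 points in the second. All four rates come from the same stage counts, so a report that shows the counts lets a reader obtain any of them.

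**4. The primary denominator.** Let k of 50 consented patients never start, and let x complete four cycles. Look for x with x/(50 − k) ≥ 0.80 and x/50 < 0.80.

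- k = 0 or 1: none.
- k = 2: x = 39 only (39/48 = 0.813, 39/50 = 0.780). The Wilson 95% CIs, 0.681 to 0.898 and 0.648 to 0.872, both include 0.80.
- k = 3: x = 38 and 39.

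With k = 1, whether the 95% CI includes 0.80 differs between 49 and 50 at two counts only, and which two depends on the method: 34 and 45 (Wilson), 33 and 44 (Wald), 33 and 45 (Clopper-Pearson). Section 7.2 names no method. With 45 starters the half-width would be 1.96 × √(0.16/45) = 0.117, against 0.111 with 50.

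**The case for a change.** The best case for an edit is that reading section 7.3 as a minimum only stops it from excluding patients. It does not say which patients form each denominator, and no other readable text defines a screened or approached set. The participation rate is then open on any reading, by a margin that could matter to someone planning the next trial. In addition, the readable text expressly requires reasons from ineligible patients (section 4.3) and withdrawn subjects (section 4.4.2), but not in so many words from those who turn down the offer or the call. A reason not recorded at the time cannot be recovered.

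Much of this is true as description. Section 7.3 is silent on these sets, and naming them would make it tidier. It still does not show that a result would come out wrong. Section 3.3 supplies the groups for both timings in plain terms and commits the study to reporting refusal reasons. Figure 3, the recruitment flow chart, is not reproduced in the text available, and neither is the case report form, so neither the denominator nor a refusal-reason field can be called absent. The size of the participation spread rests wholly on assumed losses.

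**Conclusion.** The concern does not call for a change. Section 7.3 leaves unsaid something that section 3.3 says, and an analyst following the plan as a whole would use screened patients for the eligibility rate and screening time, and offered patients for the participation rate and recruitment time. Nobody asked to tabulate reasons for refusal would report 100% participation. Which participation denominator to headline is a reporting choice in a descriptive pilot.

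The primary outcome is not at risk either. Sections 2.1 and 7.2 define its denominator as patients in whom RIC was started, and section 5.3 expects no consented non-starters. With none or one, no point estimate changes side of 0.80. The half-width of 0.11 and the target of 50 stand.

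This conclusion assumes that the screening form is completed for non-enrolled patients, as section 4.3 requires for ineligible patients and section 3.3 implies for those who refuse, and that consented non-starters are few or absent.
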